Stool, urine, and saliva sample collection: Stool samples will be collected and may be used to analyze the microbiome, polyphenol content, and polyphenol derived metabolites (table 1). Parents will be given the option to collect the child's stool sample at home. Instructions and supplies will be provided. Urine will be collected to measure wild-blueberry derived metabolites, markers of bone metabolism, and overall metabolic health. A urine sample will be collected the morning of visit #2. Urine will be collected before and following a single dose of blueberry or placebo containing foods on study visit #3. Saliva will be collected on visits #2 and #3 for metabolomics analysis. Supplies and instructions will be provided to participants.

Blood Collection After an overnight fasting, blood will be collected from a peripheral vein by a trained phlebotomist at visits #2 and #3. Up to 75 ml of blood will be collected during the entirety of the study. At visit #2, up to 16 ml (3.25 teaspoons) of whole blood will be collected following an overnight fasting. At visit #3, up to 24 ml (~1.6 tablespoons) of blood will be collected in the fasting state (baseline). After the initial blood draw, children will receive blueberry/placebo containing products. Participants will be free to drink water during this part. Eight ml (8 ml) of blood will be drawn 1 hour after the consumption of the study product while 6 ml will be drawn at 2, 3, 4, and 5 hours [Total 56 ml (24+ 32 mL) or 3.75 tablespoons on visit #3]. We may place a saline lock and administer a slow drip of saline

or lactate ringers at the first blood draw of visit #3 to minimize further needle sticks. If an IV catheter cannot be placed, and the participant agrees, standard venipuncture will be done to collect blood at baseline (fasting), and after 1- and 5 hours after eating the study product. If blood draws need to be repeated, the total amount of blood drawn for this study will not exceed 75 ml.

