technology uses sound waves (ultrasound) to visualize the diameter of the brachial artery. A baseline image of the brachial artery will be recorded at rest. Three ECG electrodes will be placed on the torso of the subject, such that ultrasound measurements will be captured at identical times during the cardiac cycle (i.e. ECG-gating of ultrasound images). A blood pressure cuff will be placed around the lower arm (the opposite arm that was used for measuring blood pressure) and the cuff will be inflated to 50 mmHg above systolic pressure for 5 minutes, followed by rapid deflation of the cuff. The diameter of the brachial artery will be measured using edge detection software (Vascular Tools, Medical Imaging Applications, IA, USA) from ultrasound images captured during the R wave of the cardiac cycle (via ECGgating) throughout the 8-minute recording protocol. The advantage of using ultrasound for FMD measurements is that this is a painless imaging test that uses non-invasive sound waves for imaging. There may be some discomfort from the blood pressure cuff since it will be applied tightly on the forearm. If the measurement is uncomfortable for the participant, and he/she requests to stop, then the procedure will be immediately aborted. FMD measurements will be done primarily by a registered clinical exercise physiologist with expertise in this procedure. However, other research staff trained and certified by [name] (Director of the vascular physiology laboratory at ACNC) may conduct this measurement. FMD will be measured in the fasted state in visits #2 and #3 and 1-2 hours after consuming a study product (visit #3 only).

Questionnaires: A food frequency questionnaire, a medical history questionnaire, selected questions form the National Survey of Children's Health, and a self-assessment questionnaire of pubertal status will be done at enrollment (12). Participants will have privacy to answer the pubertal status self-assessment questionnaire. Assessment of pubertal status is needed as measurements of bone metabolism are part of the present study. Puberty is known to dramatically affect bone turnover and metabolism (13). Physical examination for puberty staging is unacceptable outside the clinical setting thus self-assessment questionnaires have become the tool of choice in research studies.

Study Population

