Statistical analysis: Based on means and standard deviations observed in previous similar studies, our primary outcome will have in excess of 80% power to detect statistical significance among the study groups testing at the 5% level of significance. This calculation assumes that we have at least n=9 subjects in each of our four combinations of gender and blueberry status. This being the case, we propose to recruit n=11 subjects in each combination of gender and blueberry status (n=44 total, 22 per study arm) to compensate for a reasonable level of dropout that may occur. Power and sample size calculations were performed by SAS 9.4 Proc Power. [name], ACNC statistician will be in charged randomization process. Prior to analyses, data will be checked for potential outliers and aberrant measurements. Additionally, the data will be also checked for conformity with distributional assumptions of the proposed statistical models. Analysis of variance (ANOVA) or its non-parametric variants will be used to assess differences among gender and blueberry diet combinations. Significance will be declared at the 5 percent level of significance. To learn whether peak VO2 indeed modifies the effect of WBB supplementation, the potential modifier will be added into the ANOVA thus making an analysis of covariance (ANCOVA). The slope of the modifier will be allowed to depend on WBB status; that is, there will be a slope for the placebo group and one for the WBB group.

Reimbursement

The compensation per visit are \$50 for visit #1, \$50 for visit #2, and \$175 for visit #3 (Total \$275). If the participant decides not to complete the study, is unwilling, or unable to complete an assessment, a \$25 gift card or check will be provided.

In the event that blood draws or other measurements need to be repeated and rescheduled due to technical problems (but not participant refusal to blood draw), an additional \$50 gift card or check will be provided.

Ethical Considerations

This study will be conducted in accordance with all applicable government regulations and University of Arkansas for Medical Sciences (UAMS) research policies and procedures. This protocol and any amendments will be submitted and approved by the UAMS Institutional Review Board (IRB) to conduct the study. Formal consent and assent,

using the IRB-approved consent/assent form, will be obtained before the subject is

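### The only stated analysis, an ANOVA across gender-by-diet cells, has no time, child or baseline term for the serial visit 3 plasma samples or the three FMD readings

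*Combined protocol and SAP*

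**What the plan says.** **Sampling.** The Blood Collection section takes one fasting blood sample at visit 2. At visit 3 it takes a fasting sample and an 8 ml sample one hour after product. The later draws follow: "while 6 ml will be drawn at 2, 3, 4, and 5 hours". When catheter placement fails and the child is willing, the schedule shrinks to three draws: "standard venipuncture will be done to collect blood at baseline (fasting), and after 1- and 5 hours after eating the study product".

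**FMD.** The Endothelial function section measures FMD fasted at visits 2 and 3, and once more 1 to 2 hours after product at visit 3.

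**Product timing.** The Dietary Intervention section starts product on the day of visit 2 and continues it to the morning of visit 3, six days in all.

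**Analysis.** The Data Analysis section is the only analysis text: "Analysis of variance (ANOVA) or its non-parametric variants will be used to assess differences among gender and blueberry diet combinations". Its one extension adds peak VO2 as a covariate: "The slope of the modifier will be allowed to depend on WBB status". It gives no time factor, child effect, repeated-measures or mixed model, AUC or other summary measure, designated hour, baseline adjustment, multiplicity rule, or rule for children on the reduced schedule.

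**The concern.** Objective 1 is the plasma and urine metabolite profile, and the serial samples serve it. Objectives 2 and 3 compare cardiovascular markers, including FMD, between diets. An ANOVA with gender and diet as its only factors takes one value per child. The plan does not say how six, or three, values become one, or how they enter the model together. That choice would be made with the data in hand, and the obvious routes differ in error rate and in which children they use.

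The visit 2 fasting value is drawn after an overnight fast on the day product starts, so it is the natural baseline. The stated model gives it no role.

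**Working it through.** **1. Sample counts.** Visit 3 volume: 24 + 8 + 4 × 6 = 56 ml, the protocol's own total. This confirms six draws (0, 1, 2, 3, 4, 5 h). Adding 16 ml at visit 2 gives 72 ml, within the 75 ml limit. The reduced schedule has three draws (0, 1, 5 h).

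**2. The plan's power figure.** The stated power of over 80% with 9 per cell cannot be reproduced, because the Data Analysis section gives no mean, SD or effect size and does not name the primary outcome. Inverting it (noncentral t, two-sided 5%, 18 per arm) implies a detectable arm difference of about 0.96 SD for one value per child. Whether the serial samples bear on the powered comparison cannot be determined.

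**3. If all samples were pooled as independent.** Assume no diet effect, equal within-child correlation (ICC) and no common time trend. The documents give no ICC. With m samples per child:

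type I error ≈ 2 × [1 − Φ(1.96 / √(1 + (m − 1) × ICC))]

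The last column simulates the two-by-two ANOVA with 11 per cell, 20,000 data sets per setting.

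| ICC | 1 + 5 × ICC (m = 6) | Formula | Simulated |
|---|---|---|---|
| 0.3 | 2.5 | 0.215 | 0.218 |
| 0.5 | 3.5 | 0.295 | 0.306 |
| 0.7 | 4.5 | 0.356 | 0.369 |

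With m = 3 the formula gives 0.121, 0.166 and 0.206. With one value per child the simulated error is 0.050.

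**4. If each post-dose hour were tested separately at 5%.** For five independent tests the chance of at least one false positive per analyte is 1 − 0.95^5 = 0.226. Simulated with correlation it is 0.207, 0.183 and 0.148 at ICC 0.3, 0.5 and 0.7. The tests at 2, 3 and 4 h would also exclude every three-sample child.

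**5. If a trapezoid AUC were taken on whatever samples exist.** The weights are 0.5, 1, 1, 1, 1, 0.5 on six points, but 0.5, 2.5, 2.0 on 0/1/5 h. Take an assumed curve c(t) = (t/tmax) × exp(1 − t/tmax).

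- Peak at 1 h: the values at 0 to 5 h are 0, 1, 0.736, 0.406, 0.199, 0.092. Six-point AUC = 1 + 0.736 + 0.406 + 0.199 + 0.046 = 2.387. Three-point AUC = 2.5 × 1 + 2.0 × 0.0916 = 2.683. Ratio 1.12.
- Peak at 2 h: 3.177 / 3.749 = 0.85.
- Peak at 3 h: 3.335 / 3.963 = 0.84.

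For a three-sample child the shift is therefore about -16% to +12% for peaks at 1 to 3 h. Outside that range, a 4 h peak gives 0.86. A 0.5 h peak gives 1.87, but there even the six-point AUC is poor (0.983 against a true 1.358).

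**6. Baseline.** The documents give no correlation between visit 2 and visit 3 values, so the gain in precision from adjustment cannot be sized.

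**The case against.** The strongest reply is that the plan proposes none of the analyses in steps 3 to 5. That is right. A reader might infer that the trial runs at a 22% to 36% false-positive rate; the documents do not support this, since one value per child keeps 5%. ANOVA could also mean a repeated-measures form. None is specified, however, and the classical complete-case version would drop every three-sample child.

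A reader might infer that no form of the stated ANOVA can cope, or that most within-child information is lost. Neither holds. The 0, 1 and 5 h samples are common to both schedules, so one summary on that grid fits the ANOVA and includes children on both schedules. Two FMD change scores per child, one for the six-day question and one for the acute question, would also fit, and would use visit 2 FMD; the plan does not state them.

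Objective 1 is worded as characterisation. Descriptive reporting has no type I error to inflate, although mean curves and AUCs would still mix two grids.

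The AUC shift touches only three-sample children, whose share is unknown. At an assumed 20% with a 16% shift, an arm mean moves by 0.20 × 16% = 3.2%. In a randomised, blinded trial nothing shows that the share would differ by arm.

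A reader might also expect a mixed model to bring a large gain in power. Averaging five post-dose samples takes the detectable difference from 0.96 SD to 0.96 × √(ICC + (1 − ICC)/5) = 0.64, 0.74 and 0.84 SD at ICC 0.3, 0.5 and 0.7. That requires an equal diet effect at all five hours and a one-degree-of-freedom test. If the effect sits at two of the five hours, the difference needed there is 2.5 times larger, 1.6 to 2.1 SD. No general power gain is claimed.

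**Conclusion.** The point stands in limited form. For outcomes measured several times per child, the stated model has no place for time, child or the visit 2 baseline, and no rule for the reduced schedule. This is more than missing detail, because a better method is available from samples already collected.

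The size depends on what the analyst does:
- about 22% to 36% type I error if six samples are pooled (ICC 0.3 to 0.7, equal correlation, no common time trend);
- about 15% to 21% chance of a false positive per analyte from five unadjusted hourly tests (same ICC range);
- about -16% to +12% in a three-sample child's AUC (assumed curves peaking at 1 to 3 h).

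ICC, curve shape and the share of three-sample children are assumptions. The absence of the model terms does not depend on them. An effect on the powered comparison is not shown. The change is advisable rather than essential.

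**What to change.** In the Data Analysis section, for comparative analyses of multi-time outcomes:

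1. **Model.** Replace the plain ANOVA with a linear mixed model containing diet, categorical time, diet-by-time, sex and the visit 2 fasting value, using every available sample.
2. **Correlation.** Let within-child correlation vary with time (unstructured or autoregressive), not only through a random intercept. Six times need 6 × 7 / 2 = 21 unstructured parameters from at most 44 children, so name a simpler fallback.
3. **Visit 3 pre-dose value.** Keep it as a response, not a covariate, because it follows product use.
4. **Single test.** Name one post-dose contrast as the diet test.
5. **Logged concentrations.** If concentrations are logged, state how values below quantification are handled.
6. **FMD.** Analyse visit 3 fasting FMD adjusted for visit 2 FMD, and the acute post-product response as a separate question.

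An acceptable alternative to the mixed model for plasma is one summary per child on the common 0/1/5 h grid, analysed with the stated sex-by-diet model plus the visit 2 fasting value.

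The cost is slightly more analysis work and a few model degrees of freedom, with no extra blood, visits or participants. The mixed model does not recover the missing 2 to 4 h samples. It uses three-sample children on the assumption that those values are missing at random given the data observed.

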Plasma/serum may be used to measure levels of polyphenols, polyphenol-derived metabolites, and markers of cardiovascular health (e.g., lipids, glucose, etc.). Whole blood, plasma or serum from this study may be used in *in vitro* experiments to assess the immune response to blueberry compounds (e.g. blueberry phenolics and blueberry volatiles), or the response of cells that have been either purchased (e.g., mouse or human monocyte macrophages) or collected in other research studies (e.g., human derived macrophages) where immune responses in relation to nutrition in health and disease are an outcome of interest. The profile of innate and adaptive immune cells in children participating in this study enriched products will be measured with flow cytometry. In addition, immune stress tests in whole blood will be done to assess immune cell responsiveness to immune stressors. Markers of oxidative stress (e.g., plasma protein carbonyls, malondialdehyde, 8-Hydroxy-2'-Deoxyguanosine, and glutathione status, etc.), inflammation (C-reactive protein, erythrocyte sedimentation rate, and pro-inflammatory cytokines, etc.), platelet mitochondria function platelet activation/reactivity as well as metabolomics analyses (to characterize the metabolite signature associated with a dietary pattern rich in wild blueberries) may be conducted. Sexual hormones will be measured to complement assessment of pubertal status. We may conduct gene expression analyses on circulating immune cells and blood osteoblasts. We have previously shown that osteoblast senescence is delayed in mice supplemented with wild blueberries (11). Single cell RNA sequencing and/or gene expression tests such as GPR109A, osteocalcin, alkalin phosphoatase, NFkB, beta-catenin, among other. The proposed genetic analyses will not be used to diagnose disease but will be used as markers of bone, immune, and metabolic health.

Endothelial function: Endothelial Function will be measured on visits #2 and #3 using ultrasound (GE Vivid 7 Ultrasound system with 5.0-13.0 mHz linear transducer, GE Healthcare, Chicago, IL, USA) to assess brachial artery flow-mediated dilation (FMD). This

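### The bone-marker analysis uses neither pubertal status nor the visit 2 value, although the protocol says puberty strongly affects bone turnover

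*Combined protocol and SAP*

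**What the plan says.** Objective 2 includes markers of bone metabolism. The Questionnaires section has pubertal status self-assessed at enrolment and says this is needed because bone metabolism is measured: "Puberty is known to dramatically affect bone turnover and metabolism (13". Blood Collection adds a second source: "Sexual hormones will be measured to complement assessment of pubertal status". Inclusion is by age (11 to 12 years) and covers both sexes, with no restriction on pubertal stage.

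The sections on sample collection provide for urine and fasting blood at visits 2 and 3, and list bone metabolism among the uses of urine. Study product starts on the day of visit 2.

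Data Analysis is the whole analysis plan. Its main model reads: "Analysis of variance (ANOVA) or its non-parametric variants will be used to assess differences among gender and blueberry diet combinations". Peak VO2 is then added as a possible effect modifier with one slope per arm. Pubertal status and sex hormones do not appear as covariate, stratum, subgroup or sensitivity analysis. The section also does not say whether an outcome is the visit 3 value or the change from visit 2, or whether the visit 2 value enters the model.

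**The concern.** The protocol names a strong predictor of its bone outcomes, measures it before treatment and then does not use it. Any variation in a bone marker that goes with pubertal stage within each sex stays in the residual. That widens the interval for the diet effect. Arms of 18 to 22 children can also differ noticeably in pubertal stage by chance, and an analysis that ignores stage carries that difference into the diet contrast.

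What is at stake is the precision and credibility of the bone part of Objective 2. If the choice is left open, adjustment for puberty could be decided after an imbalance or a borderline result has been seen, and either choice would then be open to challenge.

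**Working it through.** **The plan's own figure.** Data Analysis states that "our primary outcome will have in excess of 80% power to detect statistical significance among the study groups", with "at least n=9 subjects in each of our four combinations of gender and blueberry status". This cannot be reproduced, because no primary outcome, difference or SD is given; the source is only "Based on means and standard deviations observed in previous similar studies". The detectable difference can be back-solved instead.

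**Inputs from the plan.** 9 per cell gives 18 per arm and 36 in total; 11 per cell gives 22 per arm and 44 in total. The significance level is 5%, taken as two-sided because sidedness is not stated.

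**Assumed inputs (not in the documents).** R2, the share of within-sex marker variance explained by pubertal stage, is 0.1 to 0.4. The visit-to-visit correlation r is 0.5 to 0.9. Puberty is taken to affect both visits equally. Half the children are past a given stage, and the stage effect is 1 SD.

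**Step 1: the model as written.** For the diet main effect in the 2x2 ANOVA, the noncentrality is d x sqrt(n/2) with n = 18 and 36 - 4 = 32 error df. Power of 80% needs d = 0.963 SD.

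**Step 2: add pubertal stage only.** The residual SD is multiplied by sqrt(1 - R2), with 31 error df. At d = 0.963:

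| R2 | SD ratio | Power |
|---|---|---|
| 0 | 1.000 | 79.9% |
| 0.1 | 0.949 | 83.9% |
| 0.2 | 0.894 | 87.9% |
| 0.3 | 0.837 | 91.7% |
| 0.4 | 0.775 | 95.1% |

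If puberty explained nothing, the cost would be about 0.1 percentage points of power.

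**Step 3: add pubertal stage on top of the visit 2 value.** With the visit 2 value alone the residual variance is 1 - r^2: 0.75, 0.51 and 0.19 at r = 0.5, 0.7 and 0.9. With both terms it is 1 - r^2 - R2 x (1 - r)^2 / (1 - R2). For r = 0.7 and R2 = 0.4 this is 0.51 - 0.4 x 0.09 / 0.6 = 0.45, so the SD falls by a further 1 - sqrt(0.45/0.51) = 6.1%. The effect is now set to give 80% power with the visit 2 value alone (31 df), and pubertal stage is then added (30 df):

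| r | R2 0.1 | R2 0.2 | R2 0.3 | R2 0.4 |
|---|---|---|---|---|
| 0.5 | 81% | 83% | 86% | 89% |
| 0.7 | 81% | 82% | 83% | 85% |
| 0.8 | 80% | 81% | 82% | 83% |
| 0.9 | 80% | 80% | 81% | 81% |

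At r of 0.7 or more, r^2 is at least 0.49. That exceeds every R2 considered, so the visit 2 value does most of the work. At r = 0.5, r^2 is 0.25, and puberty is the stronger predictor once R2 is above 0.25.

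**Step 4: chance imbalance.** The number past the given stage is binomial(n, 0.5) in each arm. The arms differ by 20 percentage points or more with probability 0.243 at n = 18 and 0.174 at n = 22. With a 1 SD stage effect, a 20-point imbalance moves the unadjusted contrast by 0.20 x 1 = 0.2 SD. With the visit 2 value in the model the shift is about 0.2 x (1 - r): 0.06 SD at r = 0.7, 0.04 at 0.8 and 0.02 at 0.9.

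**The case against.** The strongest objection is that the visit 2 value would do most of what adjustment for puberty does. Supplementation lasts about 6 days, over which pubertal stage is essentially fixed, so its effect is already in the visit 2 sample. Step 3 supports this: at a correlation of 0.7 to 0.9, puberty adds at most about 5 points of power. This limits the size of the point but does not remove it, because Data Analysis names neither a baseline covariate nor a change score.

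Sex is also already in the model and absorbs part of the pubertal difference at this age. That is true, and R2 is defined within sex for that reason. Error in self-reported stage would push R2 towards the lower end of the range.

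Three stronger readings are tempting but not supported:

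- A reader might infer that the bone comparisons are biased or that the 5% level is not held. Randomisation keeps the unadjusted comparison unbiased on average with valid type I error. Only precision and chance imbalance in this one sample are affected.
- A reader might take the 84% to 95% power, equivalent to 36/(1 - R2) = 40 to 60 children instead of 36, as the value of adding puberty to a well-specified model. Those figures apply only where no visit 2 value is used.
- A reader might infer that the plan's power claim fails. It concerns an unnamed primary outcome, which may not be a bone marker.

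In the other direction, the reference list ends with a paper on minimisation and randomisation software. The text describes no minimisation and no balancing factors, so balance on puberty cannot be assumed.

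**Conclusion.** The point holds as one of efficiency and prespecification for the bone part of Objective 2. The protocol calls pubertal status needed for its bone measurements, and its analysis then uses neither that variable nor the visit 2 value. The omission is certain from the text. Its size is not, because R2, r, the stage split and the stage effect are all assumed.

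Over the assumed ranges, puberty is worth 4 to 15 points of power where a marker has no visit 2 value in the model. Where it has one, puberty is worth about 0 to 5 points at r = 0.7 to 0.9 and up to 9 points at r = 0.5. An imbalance of 20 points or more would arise in roughly one randomisation in four at 18 per arm, or one in six at 22 per arm. The visit 2 value would remove most of the resulting shift when r is high. The change is worth making because it costs almost nothing.

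**What to change.** Add to Data Analysis:

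> Each bone-metabolism marker measured at visits 2 and 3 will be analysed by ANCOVA of the visit 3 fasting value on diet, sex, the visit 2 value (sampled before the first study product) and enrolment pubertal stage, entered as one ordinal score. The diet effect from this model is the main bone result. A marker with no visit 2 value will be adjusted for sex and pubertal stage.

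The enrolment questionnaire should supply the score because it precedes treatment; a single ordinal term suits cells of 9 to 11 children. If the team prefers not to adjust, the section should say why a variable described as needed is left out.

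The cost is a short paragraph of analysis text and about two degrees of freedom, one for pubertal stage and one for the visit 2 value. No new data and no change to study conduct are needed.
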